7. SAFETY AND TOLERABILITY ANALYSIS

Safety and tolerability assessments will include adverse events (AEs), vital signs, and pulmonary function tests. If there is a difference between the ITT set and SAF set, then all safety summaries (or analyses if applicable) will be conducted using the SAF set. Otherwise, the ITT set will be used. No formal hypothesis testing will be performed to compare differences between treatment groups.

7.1 Extent of Exposure and Compliance

The number of doses received will be summarized by treatment group. The duration of study drug administration in minutes, the reason for study drug discontinuation, and whether 100% of study drug (4 mL) was delivered will be summarized for each dose by treatment group.

7.2 Adverse Events

The AE reporting period for this study is continuous and begins at the time of randomization to study treatment and ends on Day 29. All AEs (both serious and nonserious) must be followed until resolution or until a stable clinical endpoint is reached. All measures required for AE management and the ultimate outcome of the AE must be recorded in the source documentation and in the eCRF.

AEs will be classified by SOC and PT using the most recent version of MedDRA.

7.2.1 Treatment-emergent Adverse Events

Treatment-emergent AEs are defined as those that begin or worsen after the start of study drug administration.

For adverse events with incomplete start dates, the same imputation algorithm for partial date information as described in Section 5.6 will be used for the determination of an AE being treatment emergent or not. Briefly, the unknown portions of an AE onset date will be imputed to the latest possible before being compared to the date of first study drug administration.

7.2.2 Adverse Event Severity

The severity (i.e., grade) of an AE will be assessed by the Investigator according to the definitions in the Common Terminology Criteria for Adverse Events (CTCAE) v5.0. If the AE is not specifically listed in the reference above, the following grades should be used:

- Grade 1 Mild; asymptomatic or mild symptoms; clinical or diagnostic observations only; intervention not indicated
- Grade 2 Moderate; minimal, local or noninvasive intervention indicated; limiting ageappropriate instrumental Activities of Daily Living (ADL)
- Grade 3 Severe or medically significant but not immediately life threatening; hospitalization or prolongation of hospitalization indicated; disabling; limiting self-care ADL
- Grade 4 Life-threatening consequences; urgent intervention indicated
- Grade 5 Death related to AE

7.2.3 Adverse Event Relationship to Study Drug

The Investigator must record his/her opinion concerning the relationship of the AE to study therapy (Unrelated, Unlikely, Possibly, Probably, Definitely) on the AE eCRF. See study protocol, Section 12.5 for details.

7.2.4 Serious Adverse Events

An AE or suspected adverse reaction is considered "serious" if in the view of either the investigator or sponsor, it results in any of the following outcomes:

- Death
- A life-threatening adverse event
- In-patient hospitalization or prolongation of existing hospitalization

- Persistent or significant incapacity or substantial disruption to conduct normal life functions
- A congenital anomaly/birth defect
- Intervention to prevent any one of the other outcomes listed above (based on medical judgment)

7.2.5 Adverse Event Summaries

All AEs (serious and non-serious) occurring after randomization and before the end of study, regardless of relationship to study drug, will be included and classified by SOC and PT using MedDRA.

For TEAEs, the following will be summarized and presented:

- i. An overall summary of TEAEs, which includes:
 - a. the number and percentage of subjects experiencing a TEAE
 - b. the number and percentage of subjects experiencing a TEAE by strongest relationship to study drug
 - c. the number and percentage of subjects experiencing a TEAE by greatest severity
 - d. the number and percentage of subjects experiencing a treatment-emergent SAE
 - e. the number and percentage of subjects experiencing a TEAE leading to death
 - f. the number and percentage of subjects experiencing a TEAE leading to study withdrawal
- ii. the number and percentage of subjects experiencing a TEAE by SOC and PT.
- iii. the number and percentage of subjects experiencing a potentially related TEAE by SOC and PT, where a potentially related TEAE is defined as any TEAE with a causal relationship to study drug assessed as 'Possibly Related', 'Probably Related', or 'Definitely Related'.
- iv. the number and percentage of subjects experiencing a TEAE by SOC, PT and the strongest relationship to study drug
- v. the number and percentage of subjects experiencing a TEAE by SOC, PT and the greatest severity
- vi. the number and percentage of subjects experiencing a treatment-emergent SAE by SOC and PT
- vii. the number and percentage of patients experiencing a TEAE leading to death by SOC and PT
- viii. the number and percentage of subjects experiencing a TEAE leading to study withdrawal by SOC and PT

In the overall summary of TEAEs table (i), besides tabulating the number and percentage of subjects, the total number of TEAE episodes will also be provided. If a subject has repeated episodes of a particular TEAE, all episodes will be counted in the summary table.

In the remaining summary tables, the incidence of TEAEs will be calculated by dividing the number of subjects who have experienced the event by the total number of subjects. Thus, the incidence of TEAEs is shown in terms of the total number of subjects and not in terms of the total number of episodes. If a subject has repeated episodes of a particular TEAE, only the most severe episode, or the episode with the strongest causal relationship to study drug, will be counted in the summary tables.

A subject with more than one type of TEAE in a particular SOC or PT will be counted only once in the total of subjects experiencing TEAEs in that particular SOC or PT.

All occurrences of all AEs and SAEs will be listed for each subject, grouped by treatment group. The listing will contain the following information: treatment group, verbatim term, SOC, PT, severity and grade (1-Mild, 2-Moderate, 3-Severe, 4-Life threatening, 5-Death), relationship to study drug, date and day of onset, date and day of resolution or death, action taken with regard to study drug, the outcome, whether the event was an SAE, whether it led to study withdrawal, and whether it is a TEAE. Listings will be sorted by treatment group, subject identification number, onset date, SOC, and PT. If the onset date is completely missing, then these events will be presented first. If the onset date is missing a month or a day, then these events will be presented before any complete dates.

7.3 Pulmonary Function Testing

Spirometry tests including FEV1 (L), % predicted FEV1, FVC (L), % predicted FVC and FEV1/FVC values will be collected at screening and FEV1 (L) will also be recorded at the time points presented in the Appendix A. FEV1 results will be summarized by presenting descriptive statistics of raw data of FEV1 (L) and percent change from each Pre-dose value to Post-dose value on the dosing days.

The proportion of subjects with percent decrease in FEV1 (L) from Pre-dose value to Post-dose value will be presented for each category: >10% and <=12% of reduction; >12% and <=20% of reduction; and >20% of reduction at each measurement time point (Day 1, Day 3, Day 6 and Day 10).

The percent change in FEV1 (L) from Pre-dose value to the protocol defined 30-min Post-dose values will be illustrated in a box/whisker graph on each dosing day by treatment group.

Spirometry results from unscheduled visits will be excluded from table summaries but will be included in the data listing.

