7.10.2. Day 1 (Study Drug Administration)

Dosing

PUL-042 administration must be supervised by a health care professional. PUL-042 will be administered via a PARI Sprint nebulizer equipped with a filter valve to prevent aerosol generation. A nose clip will be used during the nebulization procedure. All doses will be administered as a constant volume (4 mL) via nebulization; the nebulizer will be operated until all drug has been delivered. All of the following time points are defined relative to the completion of dosing (T_0).

Post-Dose Guidelines

In previous studies with healthy volunteers, some subjects have demonstrated a transient decrease in lung function, usually asymptomatic. To date, subjects have recovered to at or near baseline lung function values without the administration of rescue medication. However, if after administration of PUL-042 Inhalation Solution there are clinical symptoms (increased respiratory rate, cough, shortness of breath) of decreased lung function, albuterol (salbtuamol) can be administered.

Following dosing, if a reduction of FEV1 >10% relative to pre-treatment is recorded, the subject should have the FEV1 measurement repeated as clinically indicated. If a reduction of FEV1 >12% relative to pre-treatment is recorded at 4 hours, the subject must be reviewed by the Principal Investigator prior to further dosing. If a reduction of FEV1 >12% relative to pre-treatment persists for up to 4 hours and is associated with clinical symptoms over this period, no further investigational treatment should be administered. Albuterol (salbutamol) may be given to symptomatic subjects at the discretion of the investigator.

If a reduction of FEV1 >20% relative to pre-treatment is recorded, no further investigational treatment should be administered to that subject.

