7.11. Study Days 3, 6, and 10 (Study Drug Administration)

All procedures should occur ±1 day from the scheduled Study Day.

7.11.1. **Pre-dose**

On Days 3, 6, and 10 the following dosing guideline should be observed prior to dose administration:

• At Investigator discretion, dosing can be HELD or STOPPED at any time for safety reasons.

The following should be obtained prior to dosing.

- Physical examination
- Vital signs
- Spirometry
- Adverse event assessment
- Concomitant medication assessment
- SARS- CoV-2 infection symptom score
- Ordinal Scale for Clinical Improvement

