7.11.2. Days 3, 6, and 10 (Study Drug Administration)

Dosing

PUL-042 administration must be supervised by a health care professional. PUL-042 will be administered via a PARI Sprint nebulizer equipped with a filter valve to prevent aerosol generation. A nose clip will be used during the nebulization procedure. All doses will be administered as a constant volume (4 mL) via nebulization; the nebulizer will be operated until all drug has been delivered. All of the following time points are defined relative to the completion of dosing (T_0).

Note: Missed doses should not be replaced

Post-Dose Guidelines

In previous studies with healthy volunteers, some subjects have demonstrated a transient decrease in lung function, usually asymptomatic. To date, subjects have recovered to at or near baseline lung function values without the administration of rescue medication. However, if after administration of PUL-042 Inhalation Solution there are clinical symptoms (increased respiratory rate, cough, shortness of breath) of decreased lung function, albuterol (salbutamol) can be administered.

Following dosing, if a reduction of FEV1 >10% relative to pre-treatment is recorded, the subject should have the FEV1 measurement repeated as clinically indicated. If a reduction of FEV1 >12% relative to pre-treatment is recorded at 4 hours, the subject must be reviewed by the Principal Investigator prior to further dosing. If a reduction of FEV1 >12% relative to pre-treatment persists for up to 4 hours and is associated with clinical symptoms over this period, no further investigational treatment should be administered. Albuterol (salbutamol) may be given to symptomatic subjects at the discretion of the investigator.

If a reduction of FEV1 >20% relative to pre-treatment is recorded, no further investigational treatment should be administered to that subject.

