11.2. Subject Withdrawal/Lost to Follow-up

Subjects who are discontinued from dosing during the study and have received at least one dose of investigational treatment must be followed to Day 29 according to the schedule of events specified above for pre-dose assessments. There will be no post-dose assessments for these subjects.

Subjects will be free to withdraw from the study at any time without giving a reason. Subjects will be considered withdrawn from the study in the event of any of the following reasons:

- Withdrawal of the subject's consent for any reason.
- Subject lost to follow-up prior to the Study Day 29 assessments.

In the event a subject withdraws from the study for any reason, the Investigator must notify Pulmotect as soon as possible and complete the applicable eCRF pages. An effort should be made to capture the reason(s) for withdrawal.

Subjects that withdraw should complete the Early Discontinuation assessments as soon as possible.

A subject is considered lost to follow-up after 3 documented attempts to contact the subject without success.

Subjects who withdraw after the start of study drug administration will not be replaced.

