4.4 Handling of Dropouts or Missing Data

Except for the time to event endpoint (Table 1), partial end dates of prior and concomitant medications (Section 5.6), and partial onset dates of AEs (Section 7.2.1), all other missing data will be treated as missing and no method for imputation is planned.

Missing data on the time to event endpoint will have events coded as right censored per the following table:

Table 1 Missing Data Coding for Time to Event Data Analysis

Endpoint	Right Censoring
Subject Survival	Subjects who are still alive as of the last known follow-up will be
	right censored as of the date of last subject contact when the subject
	was known to be alive.

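### SAP 7.3 reports the post-dose FEV1 fall only by dosing day, so Days 3, 6 and 10 leave out subjects already stopped for a fall and lean toward a smaller effect than Day 1; a worst-fall-per-subject table is needed

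*SAP*

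**What the plan says.** The pre-dose to post-dose reduction in FEV1 is the first safety and tolerability endpoint listed in SAP 2.2.3. SAP 7.3 summarises it by dosing day only: raw litres and percent change, a box plot of the 30-minute percent change, and a categorical table. On the last it says: "The proportion of subjects with percent decrease in FEV1 (L) from Pre-dose value to Post-dose value will be presented for each category". The categories are above 10% to 12%, above 12% to 20%, and above 20%. No denominator is stated, and there is no summary over the whole course of dosing.

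Two rules in protocol 7.10.2 and 7.11.2 end dosing on the basis of FEV1:

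- "If a reduction of FEV1 >20% relative to pre-treatment is recorded, no further investigational treatment should be administered to that subject".
- A fall above 12% that "persists for up to 4 hours and is associated with clinical symptoms over this period, no further investigational treatment should be administered".

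Two others do not. After a fall above 10%, "the subject should have the FEV1 measurement repeated as clinically indicated". After a fall above 12% at 4 hours, "the subject must be reviewed by the Principal Investigator prior to further dosing". Protocol 7.11.1 adds: "At Investigator discretion, dosing can be HELD or STOPPED at any time for safety reasons".

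For subjects off dosing, protocol 7.13 and 11.2 say: "There will be no post-dose assessments for these subjects". SAP 4.4 lists a few exceptions that do not include FEV1, and then: "all other missing data will be treated as missing and no method for imputation is planned".

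Related provisions: SAP 4 gives counts and percentages for categorical variables, SAP 7.1 tabulates doses received and reasons for discontinuation, and SAP 7 plans no formal testing of safety data.

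**The concern.** Every subject in the Safety set received the first dose, so Day 1 is unselected. On Days 3, 6 and 10, a post-dose value exists only for subjects whose earlier falls did not end dosing. The later tables are thus selected on the outcome they report. If a subject's falls at successive doses are correlated, those removed are the ones likely to fall most again, and the remaining group looks better even if the drug effect is unchanged.

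Protocol 5.4 reports dose-dependent falls on PUL-042 and no comparable decline on placebo. Stopping should therefore be more frequent in the active arm, and the later-day difference between arms would be pulled toward no harm.

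What is at stake is how repeated dosing is described. A reader comparing Day 1 with Day 10 could take a smaller fall for developing tolerance when part of it is selection. The plan also gives no direct count of subjects with a notable fall at any dose.

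**Working it through.** **Inputs.** The stopping rules, the absence of later post-dose readings and the absence of imputation are as quoted above. The documents give no expected fall, SD, within-subject correlation or stopping rate, so there is no planned figure to reproduce. Protocol 5.4 says only that falls in the first phase 1 study were largely within 12%. Everything numerical below is an assumption.

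**Model.** Percent change at dose j = mean + subject effect + error, normal, with the same true mean at all four doses. A subject leaves after a fall above 20%. A second variant adds an assumed 20% chance of stopping after any fall above 12%, standing in for the persistent-and-symptomatic rule. ICC is the within-subject correlation.

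**Which settings fit the protocol's description.** The share of Day 1 falls above 12% is 1 − Φ((12 − 3)/5) = 1 − Φ(1.8) = 3.6% for mean fall 3, SD 5; and, from the simulation, about 12% for 5/6, 28% for 8/7 and 40% for 10/8. The first two settings match falls that are mostly within 12%.

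**Mean fall (%) with a constant true effect, ICC 0.3 to 0.9.**

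| Mean/SD | Day 1 | Day 10, 20% rule only | Day 10, with added stop | Apparent drop (points) |
|---|---|---|---|---|
| 3/5 | 3.0 | 3.0 | 2.8–2.9 | 0–0.2 |
| 5/6 | 5.0 | 4.8–4.9 | 4.3–4.7 | 0.1–0.7 |
| 8/7 | 8.0 | 7.1–7.5 | 6.2–7.1 | 0.5–1.8 |
| 10/8 | 10.0 | 7.9–8.8 | 6.8–8.4 | 1.2–3.2 |

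At ICC 0 no setting shows a drop.

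**Share above 20% among those still dosed, Day 1 to Day 10 (20% rule only).** 0.6% to 0.2–0.6% (5/6); 4.3% to 0.8–3.3% (8/7); 10.6% to 1.6–7.4% (10/8).

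**How often one arm of 100 would show it (added stop).** With a constant effect, the Day 10 mean fall is smaller than Day 1 in about 50% of trials at ICC 0. At ICC 0.3 to 0.9 the figure is 55–77% (3/5), 65–96% (5/6), 82–100% (8/7) and 91–100% (10/8). If the true fall deepens by 1 point per dose, the figure (ICC 0 to 0.9) is 0–9% in the first three settings and 2–80% in the last.

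**Denominator.** If all Safety-set subjects were used on later days, proportions would decline even at ICC 0. For 8/7, 87.6% are still dosed on Day 10 and 4.39% of them exceed 20%: 0.876 × 4.39% = 3.8% of all subjects, against 4.3% on Day 1.

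**Can the by-day counts give the share ever above 20%?** A subject stopped at the first such fall enters that row once. Take a 10% risk per dose, correlation 0.3, beta-binomial: a = 0.1 × 0.7/0.3 = 0.2333, b = 0.9 × 0.7/0.3 = 2.1, and the risk after k clear doses is a/(a + b + k), giving 10.0%, 7.0%, 5.4% and 4.4%. Per 100 subjects the counts are 10.0 + 90 × 0.0700 + 83.7 × 0.0538 + 79.2 × 0.0438 = 10.0 + 6.3 + 4.5 + 3.5 = 24.3. Directly, 1 − 0.900 × 0.930 × 0.946 × 0.956 = 24.3%. They agree, so this share is recoverable.

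**The same for 12%.** A subject with a fall of 12% to 20% may continue and be counted again. For 8/7, ICC 0.6, 20% rule only, the counts above 12% per 100 are 28.3 + 0.957 × 26.0 + 0.927 × 24.5 + 0.903 × 23.2 = 28.3 + 24.9 + 22.7 + 20.9 = 96.8. That counts falls, not subjects. The tables alone say only that the share ever above 12% lies between 28.3% and 96.8%. The same holds for 10%.

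**The case against.** The best reply is that little is hidden and the effect may be trivial. Falls were largely within 12% in earlier work, and protocol 7.2 excludes chronic lung disease and FEV1 below 70% of predicted, so few subjects may cross a stopping threshold. Percent change, categories and box plot are paired within subject and day. SAP 7.1 shows how many doses were given and why dosing ended. The analysis is descriptive, and neither document proposes to read the trend across days as tolerance.

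Much of this stands, and it rules out several stronger readings that a reader might infer:

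- That the fall must shrink by construction. It need not: shrinkage requires within-subject correlation and enough stopped subjects, and a real worsening can outweigh it.
- That no planned table yields the share ever above 20%. Adding the four counts and dividing by the Day 1 number gives it, provided the 20% rule is followed and the tabulated readings are the ones that triggered the stop.
- That every symptomatic fall above 12% ends dosing, or that later days contain only subjects who tolerated every earlier dose. The 12% rule also requires persistence; other falls lead to repeat measurement or review, and doses may be held.
- That stopped subjects certainly keep pre-dose spirometry, so raw pre-dose and post-dose means come from different subjects. Protocol 7.13 and 11.2 keep them on the pre-dose schedule, but 7.8 sends subjects who withdraw from dosing to the Early Discontinuation Visit and Day 29, neither of which includes spirometry. These sections need reconciling. Only raw litres would be affected.

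What the reply does not answer is that the discontinuation table is not linked to FEV1, that SAP 7.3 states no denominator, and that the shares ever above 10% and 12% cannot be obtained from the planned tables. Without a test or model, the by-day tables are the evidence.

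**Conclusion.** The point holds as a matter of selection and presentation. The Day 3, 6 and 10 FEV1 summaries are conditional on not having been stopped earlier, are biased toward a smaller fall than Day 1 whenever falls correlate within subject, and are probably more so on PUL-042. The arm direction is an inference from protocol 5.4, not a stated figure.

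The size cannot be known in advance. It is nil at zero correlation, about 0 to 0.7 points of mean fall in the settings closest to the protocol's description, and up to about 3 points with larger assumed falls. These figures rest on assumed means, SDs, correlations and a 20% symptomatic-stop rate. The documents do not support saying that the tables will show tolerance. They do support saying that a decline across days should not be read as tolerance, and that a subject-level summary is missing. This is a worthwhile, inexpensive improvement, not a defect that undermines the trial.

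**What to change.** In SAP 7.3, before unblinding:

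1. Add, as the main FEV1 safety summary, each subject's largest scheduled pre-dose to post-dose percent fall over all doses received, in cumulative categories (above 10%, above 12%, above 20%), by arm, with all Safety-set subjects as denominator. Give subjects with no paired reading their own row.
2. In each by-day table, show the number dosed and measured, and the number not dosed because of an earlier FEV1 fall or symptoms. State the denominator of the percentages.
3. Compute raw pre-dose and post-dose FEV1 means only in subjects with both values that day.

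The data are already collected and no dosing rule changes. The cost is one extra table, some SAP wording and a slightly less favourable headline FEV1 figure. A worst-of-up-to-four value also picks up measurement noise, so it should be read against the placebo column rather than alone.
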